8.2.3 Correlative Studies for Research/Pharmacokinetic Studies

N/A

8.2.4 Samples for Genetic/Genomic Analysis

N/A

8.3 SAFETY AND OTHER ASSESSMENTS

Physical examination A targeted physical examination will be performed at baseline prior to initial study product administration on Day 1. The baseline physical examination can be one that is conducted from screening to Day 1. Post-baseline physical examinations will be done only when needed to evaluate possible adverse event(s) (i.e. any new signs or symptoms). WHO bleeding assessment should be done on follow up visits. No routine physical exam is needed for study visits after Day 1.

Vital signs Vital signs will be done on each follow up visit and include temperature, blood pressure, heart rate, respiratory rate, O₂ saturation.

Assessment of adverse events.

Assessment of adverse events will be performed at each follow up visit

The results of the research studies will not be mandatorily revealed to the patients but can be provided to the patients upon request.

8.4 ADVERSE EVENTS AND SERIOUS ADVERSE EVENTS

8.4.1 Definition of Adverse Event

Adverse event means any untoward medical occurrence associated with the use of an intervention in humans, whether or not considered intervention-related (21 CFR 312.32 (a)).

8.4.2 Definition of Serious Adverse Events (SAE)

An adverse event (AE) or suspected adverse reaction is considered "serious" if, in the view of either the investigator or sponsor, it results in any of the following outcomes: death, a life-threatening adverse event, inpatient hospitalization or prolongation of existing hospitalization, a persistent or significant incapacity or substantial disruption of the ability to conduct normal life functions, or a congenital anomaly/birth defect. Important medical events that may not result in death, be life-threatening, or require hospitalization may be considered serious when, based upon appropriate medical judgment, they may jeopardize the participant and may require medical or surgical intervention to prevent one of the outcomes listed in this definition. Examples of such medical events include allergic bronchospasm requiring intensive treatment in an emergency room or at home, blood dyscrasias or convulsions that do not result in inpatient hospitalization, or the development of drug dependency or drug abuse.

Abbreviated Title: Fostamatinib for post-transplant cytopenias

Version Date: 11/28/2023

8.4.3 Classification of an Adverse Event

8.4.3.1 Severity of Event

This study will utilize the Common Terminology Criteria for Adverse Events version 5.0 (CTCAE v5.0) for toxicity and adverse event reporting. A copy of the CTCAE v5.0 can be downloaded from the https://ctep.cancer.gov/protocolDevelopment/electronic_applications/ctc.htm.

AEs will be recorded, verified, and followed until satisfactory resolution or stabilization.

Severity definitions found in the CTCAE v5.0 will be used for grading the severity (intensity) of AEs:

- 1) **Mild (Grade 1):** Asymptomatic or mild symptoms; clinical or diagnostic observations only; intervention not indicated.
- 2) **Moderate (Grade 2):** Minimal, local or noninvasive intervention indicated; limiting age-appropriate instrumental ADL*
- 3) **Severe (Grade 3):** Severe or medically significant but not immediately life-threatening; hospitalization or prolongation of hospitalization indicated; disabling; limiting self-care ADL**.
- 4) **Life-threatening (Grade 4):** Life-threatening consequences; urgent intervention indicated.
- 5) **Death (Grade 5):** Death related to AE.

*Instrumental ADL refer to preparing meals, shopping for groceries or clothes, using the telephone, managing money, etc.

**Self-care ADL refer to bathing, dressing and undressing, feeding self, using the toilet, taking medications, and not bedridden.

8.4.3.2 Relationship to Study Intervention

All grade 3 and 4 AEs, clinically significant laboratory abnormalities, and all SAEs occurring from the time of study drug initiation through the end of the 16th week must have their relationship to study intervention assessed by the investigator who examines and evaluates the participant based on temporal relationship and his/her clinical judgment. The degree of certainty about causality will be graded using the categories below. In a clinical trial, the study product must always be suspect.

- **Definitely Related** – There is clear evidence to suggest a causal relationship, and other possible contributing factors can be ruled out. The clinical event, including an abnormal laboratory test result, occurs in a plausible time relationship to study intervention administration and cannot be explained by concurrent disease or other drugs or chemicals. The response to withdrawal of the study intervention (de-challenge) should be clinically plausible. The event must be pharmacologically or phenomenologically definitive, with use of a satisfactory rechallenge procedure if necessary.
- **Probably Related** – There is evidence to suggest a causal relationship, and the influence of other factors is unlikely. The clinical event, including an abnormal laboratory test result, occurs within a reasonable time after administration of the study intervention, is unlikely to be attributed to concurrent disease or other drugs or chemicals, and follows a clinically reasonable response on withdrawal (rechallenge). Rechallenge information is not required to fulfill this definition.
- **Possibly Related** – There is some evidence to suggest a causal relationship (e.g., the event occurred within a reasonable time after administration of the trial medication). However, other factors may have contributed to the event (e.g., the participant's clinical condition, other concomitant events). Although an AE may rate only as "possibly related" soon after discovery, it can be flagged as requiring more information and later be upgraded to "probably related" or "definitely related", as appropriate.

- **Unlikely to be related** – A clinical event, including an abnormal laboratory test result, whose temporal relationship to study intervention administration makes a causal relationship improbable (e.g., the event did not occur within a reasonable time after administration of the study intervention) and in which other drugs or chemicals or underlying disease provides plausible explanations (e.g., the participant's clinical condition, other concomitant treatments).
- **Not Related** – The AE is completely independent of study intervention administration, and/or evidence exists that the event is definitely related to another etiology. There must be an alternative, definitive etiology documented by the clinician.]

8.4.3.3 Expectedness

The site principal investigator will be responsible for determining whether an adverse event (AE) is expected or unexpected. The determination will be made only for grade 3 and 4 AE, clinically significant laboratory abnormalities, and all SAEs. An AE will be considered unexpected if the nature, severity, or frequency of the event is not consistent with the risk information previously described for the study intervention in the package insert or investigator's brochure.

8.4.4 Time Period and Frequency for Event Assessment and Follow-Up

The occurrence of an adverse event (AE) or serious adverse event (SAE) may come to the attention of study personnel during study visits and interviews of a study participant presenting for medical care, or upon review by a study monitor.

Grade 3 and 4 AE, clinically significant laboratory abnormalities, and all SAEs occurring from the initiation of the study drug through the last visit will be will be captured on the appropriate case report form (CRF). All grade 3-4 AEs and all SAEs will be followed to adequate resolution, or until the investigator deems the event to be chronic or the participant is stable.

Any medical condition that is present at the time that the participant is screened will be considered as baseline and not reported as an AE. However, if the study participant's condition deteriorates and that event reaches grade 3 and above, or becomes an SAE at any time after the first dose of the study drug, it will be recorded as an AE. For the purposes of baseline documentation, a medical condition is described as a group of signs and symptoms clearly related to a disease, illness or injury; any physiologic, mental or psychological condition or disorder and will be captured as a single event.

Changes in the severity of an AE will be documented to allow an assessment of the duration of the event at each level of severity to be performed. AEs characterized as intermittent require documentation of onset and duration of each episode.

8.4.5 Adverse Event Recording

Information on grade 3 and 4 AEs, clinically significant laboratory abnormalities, and all SAEs, occurring from the initiation of the study drug through the last visit will be recorded on the appropriate CRF. All clearly related signs, symptoms, and results of diagnostic procedures performed because of an AE should be grouped together and recorded as a single diagnosis. If the AE is a laboratory abnormality that is part of a clinical condition or syndrome, it should be recorded as the syndrome or diagnosis rather than the individual laboratory abnormality. Each AE will also be described in terms of duration (start and stop date), severity, association with the study product, action(s) taken, and outcome. Clinician's assessment of severity, relationship to study product should be assessed only by those with the training and authority to make a diagnosis.

8.4.6 Serious Adverse Event Reporting

The study investigator will report any SAE to the Data Coordinating Center (DCC)/study sponsor (NHLBI) no later than 72 hrs after the investigator becomes aware of the SAE, whether or not considered

Abbreviated Title: Fostamatinib for post-transplant cytopenias

Version Date: 11/28/2023

study-intervention related, including those listed in the protocol or package insert and must include an assessment of whether there is a reasonable possibility that the study intervention caused the event.

All SAEs will be followed until satisfactory resolution or until the site investigator deems the event to be chronic or the participant is stable. Other supporting documentation of the event may be requested by the Data Coordinating Center (DCC)/study sponsor and should be provided as soon as possible.

SAEs from all sites will be reported to the IRB of record (NIH IRB) in accordance with the Policy 801. The sites should report SAE locally in accordance with institutional requirements.

IND safety reports will be submitted to FDA by the IND sponsor in accordance with 21 CFR 312.

Rigel Pharmaceuticals:

Data Coordinating Center (DCC)/study sponsor (NHLBI) will provide Rigel with copies of SAEs as per the schedule in the following table.

Type of Report	Timeline (Calendar Days from Awareness Date)	Format	Means of Exchange
Fatal or life threatening Suspected Unexpected Serious Adverse Reactions (SUSARs) using Rigel Compound	Copies of all IND Safety Reports will be submitted to Rigel concurrently with their submission to the FDA.	Medwatch Form	
Other SUSARs using Rigel Compound	Copies of all IND Safety Reports will be submitted to Rigel concurrently with their submission to the FDA.	Medwatch Form	Email: [contact] [contact]
Pregnancy reports	30 Days	Medwatch Form	
All other SAEs using Rigel Compound	Promptly, but no later than 15 Days	Medwatch Form	

NHLBI Clinical Director: Data Coordinating Center (DCC)/study sponsor (NHLBI) will refer to NHLBI DIR Policy to determine Clinical Director reporting requirements and timelines.

8.4.7 Events of Special Interest

The following clinical and laboratory characteristics will be followed closely: blood pressure, diarrhea, hemoglobin, ANC, platelet count, AST, ALT, total bilirubin, direct bilirubin, LDH.

8.4.8 Reporting of Pregnancy

Pregnancy is not an AE. However, any pregnancy that occurs during study participation should be reported to the IND Sponsor on the appropriate CRF (see 8.4.6). Pregnancy should be followed to outcome.

8.5 UNANTICIPATED PROBLEMS

8.5.1 Definition of Unanticipated Problems (UP)

Any incident, experience, or outcome that meets all of the following criteria:

- Unexpected in terms of nature, severity, or frequency given (a) the research procedures that are described in the protocol-related documents, such as the Institutional Review Board (IRB)-approved research protocol and informed consent document; and (b) the characteristics of the participant population being studied; and
- Related or possibly related to participation in the research (“possibly related” means there is a reasonable possibility that the incident, experience, or outcome may have been caused by the procedures involved in the research); and
- Suggests that the research places participants or others (which may include research staff, family members or other individuals not directly participating in the research) at a greater risk of harm (including physical, psychological, economic, or social harm) than was previously known or expected.

8.5.2 Unanticipated Problem Reporting

The investigator will report unanticipated problems (UPs) to the NIH Institutional Review Board (IRB) as per Policy 801.

8.5.3 NIH IRB Reporting of IND Safety Reports

Only IND Safety Reports that meet the definition of an unanticipated problem will need to be reported to the NIH IRB according to Policy 801.

9 STATISTICAL CONSIDERATIONS

9.1 STATISTICAL HYPOTHESIS AND SAMPLE SIZE DETERMINATION

This study will use a Simon two-stage minimax design [23] to test the null hypothesis (H_0) that the response rate after 12 week (primary endpoint defined in Section 3) is $\leq 10\%$ versus a one-side alternative. If the true response rate, meaning the rate of meeting the primary endpoint at 12 weeks, is 35%, the following two-stage design would have a power of 86% with a type 1 error of 0.05.

In the first stage, the study will enroll 11 subject. If ≤ 1 subjects achieve a response, the study will stop for futility and H_0 is not rejected. If 2 or more subjects achieve a response, the study will proceed to the second stage and enroll an additional 9 subjects for a total of 20 evaluable subjects. The H_0 will be rejected, meaning that the study is not futile, if more than 4 responses are observed in 20 subjects.

Subjects who discontinue treatment before completing 4 weeks, with discontinuation being unrelated to the treatment-related adverse event or disease progression will not be evaluated for the primary endpoint. Early discontinuation within 12 weeks due to toxicity or AE related to the study drugs or disease progression is counted as non-response towards the primary endpoint and these subjects will not be replaced. Safety will be assessed in subjects who received at least one dose of fostamatinib. Up to 8 additional subjects may be enrolled to account for treatment discontinuations before completing 4 weeks for reasons unrelated to treatment or disease progression. Early discontinuation within 12 weeks due to toxicity or AE related to the study drugs is counted as non-response towards the primary endpoint and these subjects will not be replaced.

Abbreviated Title: Fostamatinib for post-transplant cytopenias

Version Date: 11/28/2023

9.2 POPULATIONS FOR ANALYSES

9.2.1 Evaluable for response

Only those patients who have completed at least 4 weeks of fostamatinib treatment will be considered evaluable for response. These patients will have their response classified according to the definitions in section 3). Subjects who discontinue treatment before completing 4 weeks (unrelated to treatment or disease progression) will not be evaluated for treatment response. Early discontinuation within 12 weeks due to toxicity or AE related to the study drug will be considered as evaluable and counted as non-response.

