Study Population:	This trial is intended to include adult patients with post hematopoietic stem cell transplant immune-mediated anemia, thrombocytopenia, or both (Evans syndrome) evaluated on or after day 60 post transplantation.
Phase:	Phase II

Abbreviated Title: Fostamatinib for post-transplant cytopenias

[figure not shown]
Version Date: 11/28/2023

Description of Sites/Facilities Enrolling Participants:	This will be a multi-center study. Enrollment will take place at the NIH Clinical Center and at up to three additional participating sites. We will enroll a total of 20 patients. The study will be conducted exclusively in the United States. Data Coordinating Center (DCC): National Heart, Lung and Blood Institute (NHLBI)
Description of Study Intervention:	The study intervention is fostamatinib, an inhibitor of spleen tyrosine kinase that will be prescribed orally at a dose of 100 mg twice daily for 4 weeks followed by a hematological response assessment. On the week 4 evaluation visit, a) if cytopenias improve (hemoglobin \geq 10 g/dL, platelets \geq 50 x 10 ⁹ /L), patients will continue the same dose for a total of 12 weeks, b) if refractory cytopenias persist (hemoglobin $<$ 10 g/dL, platelets $<$ 50 x 10 ⁹ /L), fostamatinib dose will be increased to 150 mg BID. The duration of the study is 12 weeks with the option to enrol patients who respond on an extended access trial
Study Duration:	This study will enroll over 48 months followed by an additional 4months for data analysis
Participant Duration:	An individual subject will complete the study in 15 weeks, from screening at week -1 or 0 to follow-up on week 14 \pm 3 days.

Abbreviated Title: Fostamatinib for post-transplant cytopenias

Version Date: 11/28/2023

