3 STUDY DESIGN

3.1 OVERALL DESIGN

Our plan is to study fostamatinib for the treatment of immune-mediated posttransplant cytopenias (anemia, thrombocytopenia or both)

- This will be a multicenter, open label, phase II study, with no control arm with the primary objective to test the efficacy of fostamatinib in the treatment of posttransplant cytopenias.
- All study participants will receive fostamatinib 100 mg BID for 4 weeks. On the 4-week evaluation, a) if the cytopenia improves (hemoglobin ≥ 10 g/dL, platelets $\geq 50 \times 10^9/L$), patients will continue the same dose for a total of 12 weeks b) if refractory cytopenias persist (hemoglobin < 10 g/dL, platelets $< 50 \times 10^9/L$), subjects will increase dose to 150mg BID. Subjects with persistent (≥ 2 readings, 2 weeks apart) loss of hematologic response after week 5 can increase the study drug dose to 150mg BID until they are at the end of the study on week 12.
- This trial will be done primarily in an outpatient setting. Follow up visits will be completed as outpatient in-person visits at the participating site or via telehealth or telephone if patients are unable to travel for any reason, with labs drawn by local providers in this circumstance.
- The 4-week assessment is the first milestone where dose can be adjusted if necessary. At the end of the trial, participants with objective hematologic recovery will be given the option to enroll onto an extended access trial, including:
 - Post-transplant anemia who achieved a hemoglobin ≥ 9 g/dL (or 1 g/dL above baseline) without transfusion support, at least once in the 12-week phase II study period

Abbreviated Title: Fostamatinib for post-transplant cytopenias

Version Date: 11/28/2023

- Post-transplant thrombocytopenia who achieved a platelet count $\geq 30 \times 10^9/L$ (or $10 \times 10^9/L$ above baseline), without transfusion support, at least once in the 12-week phase II study period
 - Either of the above in subjects with Evans syndrome
- The plan is to treat and include a total of 20 patients in the analysis in this single arm trial.

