7.2 PARTICIPANT DISCONTINUATION/WITHDRAWAL FROM THE STUDY

Prior to removal from study, effort must be made to have all subjects complete a safety visit approximately 14 days following the last dose of study therapy.

- Participants are free to withdraw from participation in the study at any time upon request.
- Participants can be taken off study at any time per site principle investigator discretion (e.g. for significant noncompliance or if the PI believes it would be in the subject's best interest).
- Patients rolled over to Extended Access protocol 000760 will be discontinued from this protocol.

The reason for participant discontinuation or withdrawal from the study will be recorded on the Case Report Form (CRF). Subjects who sign the informed consent form but do not receive the study intervention may be replaced.

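### The first sentence of 9.2.1 contradicts the rule that early drug-related stops are evaluable non-responses, and no response rate over all dosed patients is planned

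*Combined protocol and SAP*

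**What the plan says.** **Who is evaluable.** Section 9.2.1 begins: "Only those patients who have completed at least 4 weeks of fostamatinib treatment will be considered evaluable for response". It then takes patients who stop before 4 weeks for reasons unrelated to treatment or disease progression out of the response evaluation. It ends: "Early discontinuation within 12 weeks due to toxicity or AE related to the study drug will be considered as evaluable and counted as non-response".

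**The rule in 9.1.** "Early discontinuation within 12 weeks due to toxicity or AE related to the study drugs or disease progression is counted as non-response", and such patients are not replaced. The same rule is repeated at the end of 9.1 without disease progression.

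**Replacement.** Section 9.1 adds: "Up to 8 additional subjects may be enrolled to account for treatment discontinuations before completing 4 weeks", where the reasons are unrelated to treatment or progression.

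**All-dosed set.** It is named for one purpose: "Safety will be assessed in subjects who received at least one dose of fostamatinib". Section 9.2 defines a single population, evaluable for response. Sections 9.3.1 and 9.3.2 plan no response rate over all dosed patients.

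**Enrolment.** The Synopsis says "We will enroll a total of 20 patients". Section 3.1 says "The plan is to treat and include a total of 20 patients in the analysis in this single arm trial".

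**The concern.** There are two separate problems.

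The first is a contradiction. A patient who stops at week 2 for drug-related toxicity is not evaluable under the first sentence of 9.2.1. Under its last sentence and under 9.1, the same patient is an evaluable non-responder. Section 9.2.1 is the only place where the response population is defined, so an analyst could apply its first sentence as written. The patients lost would be treatment failures, so the error would favour the drug.

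The second is a gap. The patients behind the 8 extra places had started the drug, because the text speaks of treatment discontinuations. Never-dosed patients have their own rule in 7.2 ("Subjects who sign the informed consent form but do not receive the study intervention may be replaced"). In an open-label, single-arm trial, whether an early stop was unrelated is a judgement. If those patients would mostly have failed, the evaluable rate overstates the rate among patients who started treatment, and no planned table would show the difference.

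**Working it through.** **1. The plan's own figures.** Inputs from 9.1: stage 1 n = 11, continue at 2 or more responses; total n = 20, reject at 5 or more; null rate 10%, alternative 35%.

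P(reject | p) = sum over x = 2 to 11 of Bin(x; 11, p) × P(at least 5 − x responses in 9; p), the second factor being 1 for x of 5 or more.

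- p = 0.10: 0.0397, within the stated 0.05.
- p = 0.35: 0.860, matching the stated 86%.

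The sample size is not in error.

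**2. Early stops (before 4 weeks), text against text.**

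| Reason for stop | 9.2.1, first sentence | 9.2.1, rest | 9.1 |
|---|---|---|---|
| Drug-related toxicity | not evaluable | evaluable non-response | non-response, not replaced |
| Disease progression | not evaluable | kept out of the excluded group, but not named as non-response | non-response in one sentence, omitted from the repeat |
| Unrelated | not evaluable | not evaluated | not evaluated; up to 8 extra enrolled |

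Only the third row is consistent throughout.

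**3. What the literal first sentence would do.** Assumptions: a fraction t of patients stop for related toxicity before week 4, the response rate with those patients counted as failures is 10%, and 20 completers are analysed. The completer rate is then 0.10/(1 − t).

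| t | Completer rate | P(reject) |
|---|---|---|
| 5% | 10.5% | 0.048 |
| 10% | 11.1% | 0.058 |
| 15% | 11.8% | 0.071 |
| 20% | 12.5% | 0.088 |

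The documents give no value for t.

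**4. Effect of the unrelated exclusions on the estimate.** With all 8 extra places used, 20 + 8 = 28 patients are enrolled. Take the smallest positive result, 5 responders, and count all excluded patients as non-responders (Clopper-Pearson intervals):

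- 5/20 = 25.0%, 95% CI 8.7 to 49.1%.
- 5/28 = 17.9%, 95% CI 6.1 to 36.9%.

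**5. Direction.** Suppose the all-dosed rate is 10%, k patients are excluded, and excluded patients would respond at f times that rate. The evaluable rate is [0.10 × (20 + k) − k × f × 0.10]/20.

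| f (assumed) | k = 4: rate, chance of success | k = 8: rate, chance of success |
|---|---|---|
| 0 | 12.0%, 7.6% | 14.0%, 12.8% |
| 0.5 | 11.0%, 5.6% | 12.0%, 7.6% |
| 1 | 10.0%, 4.0% | 10.0%, 4.0% |
| 1.5 | 9.0%, 2.7% | 8.0%, 1.7% |

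The effect can go either way, and the documents do not say which row applies.

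**The case against.** The strongest reply is that the contradiction is editorial. Section 9.1 states the rule clearly, the last sentence of 9.2.1 repeats it for toxicity, and excluding and replacing early unrelated stops is specified in advance. Much of that stands: the intent can be recovered and the exclusion is a legitimate design choice. It does not make the first sentence of 9.2.1 correct, and it does not supply the missing response rate. The omission of disease progression is indeed a matter of tidying, since 9.1 names it as non-response and 9.2.1 does not place it in the excluded group.

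A reader might go further in four ways that the documents do not support.

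- *That the type I error is breached.* The plan tests the rate in 20 evaluable subjects, and for that rate the error is 4.0% whatever the number excluded. The table in step 5 concerns the all-dosed rate, which the plan does not test.
- *That 8 patients will be excluded, or that at most 8 can be.* Eight limits extra enrolment. It neither predicts nor caps exclusions.
- *That nothing would document why a patient stopped.* Section 7.1 records the reason for discontinuation and any adverse event when drug is stopped. What is missing is narrower: 8.4.3.2 requires a causality category only for grade 3 and 4 events, clinically significant laboratory abnormalities and serious events, and no section says which categories count as related for the evaluability rule.
- *That 3.1 and 7.2 also contradict 9.1.* Section 3.1 can largely be read as 20 analysed, and 7.2 concerns patients never dosed. Only the Synopsis clearly mismatches.

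**Conclusion.** The point holds in this limited form. The first sentence of 9.2.1 is wrong as written and, applied literally, would drop early toxicity failures that 9.1 counts. The plan also has no response rate over all dosed patients, although up to 28 may be enrolled for 20 evaluable, and the Synopsis does not reflect this.

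The possible size is a drop from 25.0% to 17.9% at the success boundary. That figure assumes that all 8 extra places are used, that each corresponds to one excluded patient, and that all of those count as failures. With fewer exclusions the gap is smaller. The gap between two denominators is not by itself evidence of bias: there is none if exclusion is unrelated to outcome, and it reverses if excluded patients would have done better. The design, its power and its decision rule are sound. These are corrections that should be made before outcomes are known, not a reason to redesign the trial.

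**What to change.** (a) Replace the first sentence of 9.2.1 and use the same text in 9.1: *Evaluable = all patients with at least one dose, except those stopping before completing 4 weeks for documented reasons unrelated to treatment or disease progression; stops within 12 weeks for related toxicity or disease progression are non-responses and are not replaced.* Delete the repeated last sentence of 9.1.

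(b) Keep the rule of stopping at 1 or fewer of 11 and rejecting above 4 of 20. Add a descriptive response rate with exact interval in all dosed patients, counting excluded patients as non-responders unless stable recovery is documented. Label it a conservative bound, since it cannot show whether exclusion was informative. List each exclusion with its week and reason.

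(c) Optional: record the 8.4.3.2 causality category for any adverse event that leads to permanent stopping, whatever its grade, and state which categories count as related for evaluability. The cut-off is the sponsor's choice. In making it, note that 6.1.2.3 uses the probable and definite categories when it defines intolerance for grade 3 and 4 events.

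(d) Correct the Synopsis, and clarify 3.1, to *20 evaluable, up to 28 enrolled*.

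Cost: wording in four sections, one table and one listing, plus one data item if (c) is adopted. The supportive rate will usually be lower than the evaluable rate. Because 6.1.2.3 and 7.1 take some patients off study, later recovery will not always be documented, which is a further reason to present that rate as a bound.
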